3.2 Allocation to Treatment Groups and Blinding

Following consent, confirmation of eligibility, and the study Run-in phase (2-weeks to confirm that the participants' technology is functioning appropriately and 2-weeks to collect baseline data on the participants' adherence), patients will be assigned to one of three arms for the *Experiment* phase of the study using a 2:1:2 randomization scheme.

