Secondary analysis: We will construct adherence trajectories for the combined *Experiment + Observation* interval for each study participant using group based trajectory modeling (GBTM). This modeling approach accounts for changing behavior over time and allows for identification of several distinctive developmental progressions without imposing the requirement that they vary normally about the population mean.^{21,22} Thus, participants with similar daily adherence trajectories are grouped about similar longitudinal trends and the model output is probabilistic assignment of each individual to one of several (up to six) adherence groups. Based on group-based modeling research on medication adherence from other conditions, anticipated ICS trajectory groupings will likely include: (1) severe early non-adherence, (2) severe delayed non-adherence, (3) moderate or episodic non-adherence, and (4) sustained adherence.^{23,24} (See Figure 3 for a preliminary 3-group ICS adherence trajectory model from our prior work.) Adherence group/category will then become the dependent variable for subsequent analysis in which a multinomial or ordered logistic regression will be applied with treatment arm as the exposure, adjusting for the covariates

[figure not shown]

Figure 3: 30-day post-discharge ICS adherence trajectories. (From Kenyon, et al. *J Asthma*. 2018.)

described above. For each adherence trajectory group, relative risk ratios for arms 1 and 2 compared to arm 3 will be calculated. We will test for overall effect of treatment arm on adherence trajectory in addition to important permutations (i.e. Arm 1 compared to Arm 3 within sustained adherence trajectory) using chi-square tests and generate marginal estimates of the probability of trajectory group membership, given treatment arm assignment (e.g. the probability of being in the sustained trajectory group if randomized to Arm 1 vs Arm 2 vs Arm 3). Findings presented alongside the primary analysis of observed-to-prescribed interval adherence percentage.

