4.17 Sample Size and Power

Our analysis of pilot data demonstrates a 48% difference in ICS adherence when comparing a time interval with financial incentives (the same schema proposed in this study) to a time period without incentives. To ensure a power of 80% at a significance level of 0.05 to detect a more conservative 30% difference in average adherence between arms 1 and 3 in the *Experiment* phase (corresponding to 65% and 35%, respectively), 40 patients are required in each of these two arms. To ensure scientific rigor given the vulnerable nature of the population, we estimate ~20% loss to follow-up. Therefore, we will aim to enroll 50 participants in study arms 1 and 3 and 25 participants in arm 2, or 125 participants total, to achieve sufficient power to detect a difference between arms 1 and 3. The study is not to be powered to detect differences in arms 1 to 2 or 2 to 3 (hence the 2:1:2 randomization schema) or for health outcomes or cost offset; rather, it is intended to obtain preliminary estimates of marginal effects of the intervention components and effect sizes on utilization outcomes by comparing arm 1 to 2 and 2 to 3 to power a future multicenter study. Baseline data reveals that ~50% of children with at least 2 prior hospitalizations have a repeat ED visit or inpatient stay 6 months after the 2nd hospital discharge.

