ICS adherence trajectories will be characterized using group-based trajectory modeling (GBTM). GBTM is an analytic technique used to identify and characterize differential patterns of changing behavior over time in a population of interest. In GBTM, an individual is assumed to belong to only one group, of which each group has its own trajectory. I will specify several models with different number of groups (e.g. 2 to 5) using quadratic trajectories (or possibly higher order polynomials) and compare these models to identify the one that best fits our ICS use data based on both the Bayesian information criterion and group percentages that are sufficiently large (e.g. >5% of the entire sample) to ensure study power as well as model stability. The group-based trajectory modeling will be performed using PROC TRAJ macro implemented in SAS (SAS 9.3).

Once adherence trajectory groups have been determined, I will first use bivariate multinomial or ordered logistic regression models to estimate odds ratios (ORs) for the three predictors of interest, as well as baseline demographic, clinical, and health utilization characteristics, on trajectory group membership. When applying the ordered logistic regression, I will check the proportional odds assumption using the Brant test. All variables that are not marginally predictive of any trajectory group in bivariate analyses ($P\text{-value} > 0.2$) will not be included in the multivariable analysis. I will then construct a final multivariable multinomial regression model of trajectory of all marginally predictive covariates, first including (1) baseline demographic and clinical characteristics, then (2) study arm, and lastly, (3) the three hypothesized potential mechanisms.⁷ Mediation analysis will be conducted with variables associated with both study arm and trajectory membership. Covariance matrices will be generated and regression estimates standardized to obtain an overall mediated effect of each potential mechanism variable (e.g. child self-efficacy) on each study arm. The percentage of the total effect of study arm that is mediated by child self-efficacy, for instance, will be calculated using standardized beta estimates.⁸ If self-efficacy, shared responsibility, and habit index are not associated with study arm or adherence trajectory, I will then assess the additional behavioral constructs described in the “Covariates” section (medication beliefs,

[figure not shown]

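### A trajectory group of just over 5% of the sample is 6 or 7 children across three arms, which secures neither power nor stable arm ratios; separately, the any-group P-value screen overfits the Aim 2 model

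*Combined protocol and SAP*

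**What the plan says.** In Section 4.18 (Aim 2) several trajectory models are fitted, with 2 to 5 groups as the example. One is chosen by BIC together with "group percentages that are sufficiently large (e.g. >5% of the entire sample) to ensure study power as well as model stability". Section 4.16.2 allows up to six groups. It then makes trajectory group the dependent variable of a multinomial or ordered logistic regression on study arm, and for each group "relative risk ratios for arms 1 and 2 compared to arm 3 will be calculated". Adherence trajectory is also a listed secondary endpoint (Section 4.15).

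For the Aim 2 model, Section 4.18 sets a covariate screen: "All variables that are not marginally predictive of any trajectory group in bivariate analyses" (P above 0.2) are left out. The final multinomial model takes the retained covariates, then study arm, then the three proposed mechanisms.

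The only power statement with a calculation behind it is in Section 4.17. It concerns mean adherence in Arm 1 versus Arm 3, and the plan is to "enroll 50 participants in study arms 1 and 3 and 25 participants in arm 2, or 125 participants total".

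**The concern.** The sentence on group size credits a 5% share with two properties, power and stability, and no calculation in the documents supports the first. The planned ratios depend on the number of children in each arm-by-group cell, not on the group's share of the whole sample. With 6 or 7 children divided 2:1:2, a cell can easily be empty, and its maximum-likelihood ratio then has no finite, non-zero value. The documents give no minimum cell count and no rule for sparse cells.

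The screen is a separate matter. A covariate stays if it reaches P≤0.2 for any one group, so it has several chances to enter. The final Aim 2 model can then hold many parameters against few children in its smallest group. At stake are a secondary endpoint and the Aim 2 results.

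**Working it through.** **Inputs.** Arms of 50/25/50, total 125, and "we estimate ~20% loss to follow-up" (Section 4.17); allocation "using a 2:1:2 randomization scheme" (Section 3.2); the example floor of more than 5% (Section 4.18). After 20% loss in each arm, 40/20/40 = 100 remain.

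**The plan's own figure.** Section 4.17 says "40 patients are required in each of these two arms" for 65% versus 35%, 80% power and alpha 0.05. The unpooled two-proportion formula gives (1.96 + 0.8416)² × (0.65×0.35 + 0.35×0.65) / 0.30² = 7.849 × 0.455 / 0.09 = 39.7, so 40; and 40/0.8 = 50. The figure reproduces, but it does not cover the trajectory analysis.

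**Smallest passing group.** 5% of 125 is 6.25, so 7 children; 5% of 100 is 5.0, so 6. Expected counts by arm are 7 × (0.4, 0.2, 0.4) = 2.8/1.4/2.8, and 6 × (0.4, 0.2, 0.4) = 2.4/1.2/2.4.

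**Empty arms when arm has no effect.** For a group of g children among N, an arm of size n has none of them with probability C(N−n, g)/C(N, g). Inclusion-exclusion then gives the chance that at least one arm is empty.

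- 7 of 125: Arm 1 0.0249, Arm 3 0.0249, Arm 2 0.2007; Arms 1 and 2 both empty 0.00125, the same for Arms 2 and 3, Arms 1 and 3 negligible. Any arm empty: 2×0.0249 + 0.2007 − 2×0.00125 = 0.248. Arm 1 or 3 empty: 0.050.
- 6 of 100: Arms 1 and 3 0.0420 each, Arm 2 0.2521; each overlap with Arm 2 0.0032. Any arm empty: 2×0.0420 + 0.2521 − 2×0.0032 = 0.330. Arm 1 or 3 empty: 0.084.

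| Group | Any arm empty | Arm 1 or 3 empty |
|---|---|---|
| 7 of 125 | 25% | 5% |
| 6 of 100 | 33% | 8% |
| 13 of 125 | 4.8% | 0.2% |
| 19 of 125 | 1.0% | <0.1% |

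**Precision when no cell is empty.** Assume a reference trajectory group of 25% of 125 (31.25 children, 12.5/6.25/12.5 by arm) and 7 children in the small group. The standard error of the log ratio is:

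- Arm 1 versus 3: √(2/2.8 + 2/12.5) = 0.935. The 95% interval spans a factor of exp(1.96×0.935) = 6.3 either side. The ratio detectable with 80% power is exp(2.80×0.935), about 14.
- Arm 2 versus 3: √(1/1.4 + 1/2.8 + 1/6.25 + 1/12.5) = 1.145, a factor of 9.4 either side.

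With a reference group of 25 to 40%, and 7 of 125 or 6 of 100, these factors run from about 6 to 7 and from about 9 to 12. The detectable ratio for Arm 1 versus 3 is about 12 to 17.

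**The screen (Aim 2 model only).** With K groups there are K−1 contrasts. If these were independent, a noise covariate would pass with probability 1 − 0.8^(K−1): 49% for four groups and 59% for five. The contrasts share a reference group, so simulation is a better guide. With four groups it gave 38% to 49%, depending on assumed group sizes, against a nominal 20%.

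**Model size.** The intercept, two arm terms and three mechanisms (one term each) are 6 parameters per equation before any covariate, against 6 or 7 children in the smallest group. In simulated fits with four or five groups and 6 to 10 noise covariates (all assumed), the small group's arm coefficients were unstable or not estimable in 23 to 38% of runs. Further fits gave 29 to 37%, falling to about 5% with 13 children and 0% with 19.

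**The arm test.** With 125 children, groups of about 10/20/35/35%, 12 noise covariates and about 300 runs, the overall arm test at 0.05 rejected in 5.7% of null runs after screening and 3.7% unadjusted (Monte Carlo error about 1.3 points).

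**The case against.** The strongest reply is that 5% is only an example. The operative criterion is that groups be large enough, and BIC is applied alongside it. Section 4.16.2 anticipates about four groups and shows a preliminary three-group model, so nothing predicts a group at the floor. This stands: the problem is conditional on such a group being kept. One may add that stability could refer to the trajectory model itself rather than the later regression. That may be so, but it does not rescue the claim about power.

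The empty-cell risk also falls mainly on Arm 2, and Section 4.17 already says that comparisons involving Arm 2 are not powered and that preliminary estimates are sought. A reader might infer that the Arm 1 versus 3 ratio will often be inestimable; the 5% and 8% figures do not support that.

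A reader might also infer that the screen distorts the secondary-endpoint analysis. Section 4.16.2 does not use it; it belongs to the Aim 2 model. Nor do the simulations show that screening makes the arm test anticonservative: 5.7% against 3.7% is within what chance could produce.

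Parts of the plan are robust already. The overall arm test and the marginal membership probabilities in Section 4.16.2 stay usable with an empty cell. Ordered logistic regression, where used, gives a binary or continuous covariate a single P-value (a 20% pass rate), and an empty cell need not make its estimate infinite. The final Aim 2 model, however, is stated as multinomial.

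**Conclusion.** The point holds in a limited form and is minor. A share just over 5% does not ensure power: it means 6 or 7 children, at least one empty arm in 25 to 33% of cases under no arm effect, and wide intervals otherwise. The difficulty largely disappears by 13 to 19 children. It arises only if a group near the floor is retained. The counts use assigned membership, while software reports model-estimated shares that may differ by a child or so.

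The screen is a second, independent weakness, confined to Aim 2. It admits about 40 to 50% of noise covariates with four groups, overfits the model, and makes the P-values of the screened covariates too small. The number of candidates, group sizes and reference share are assumptions, because the documents do not give them.

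It would be tempting to conclude that the plan needs a higher fixed floor, such as 15%, with small groups merged into the nearest one. The material does not require that: the threshold would be a judgement, and merging would override the model chosen by BIC and could hide a distinct pattern. The primary analysis and its sample size are not affected.

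**What to change.** Amend the SAP wording before trajectory groups are examined:

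1. In Section 4.18, delete the statement that a share above 5% ensures power.
2. Make sustained versus not sustained trajectory the main arm contrast. Hypothesis 2 already targets the sustained trajectory, and the Aim 3 interview analysis already uses this split.
3. Label relative risk ratios for smaller groups as descriptive, and use penalised (Firth-type) estimation where an arm-by-group cell is empty.
4. Replace the P>0.2 screen with a short pre-specified list of baseline covariates already collected, for example run-in adherence, age and prior-year exacerbations. Always include study arm and the three mechanisms.

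The cost is a few sentences and no new data. The downside is less detail on small trajectory groups, and other baseline characteristics would be reported from the bivariate models only.

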3.1.2 Run-in Phase (Month 0)

The study will be broken down into three discrete phases: (1) *Run-in* (2) *Experiment*, and (3) *Observation* (Figure 2). During the *Run-in* phase, every caregiver-child dyad will have access to the inhaler sensor app and will receive electronic ICS use monitoring. ICS use will be monitored using an electronic sensor that affixes to their ICS inhaler and will remain through the study *Observation* phase. Participants will be sent 4 text messages, each designed to elicit a response from the caregiver about the study technology or the study itself. (See Appendix 1 for content of the Run-in text messages) Participants for whom any inhaler use data is transmitted to the study platform within the first 2 weeks of the Run-in Phase AND reply to one or more of the 4 text messages sent from the study platform (“Responders”) will be randomized into one of three arms at the end of the Run-in phase. (see section 4.10 for details on procedures for “Non-responders”) The second two weeks of the Run-in Phase is designed to provide baseline adherence data.

[figure not shown]

Figure 2: Study schema for proposed RCT

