4.11.2 Other Evaluations, Measures

The following instruments (or question blocks from the following instruments) will be used to assess key constructs at each study visit:

- Child and parent self-efficacy, measured using the Child and Parent Asthma Management Self Efficacy scale¹⁸,
- Parent/child responsibility for asthma care measured using the Asthma Responsibility Questionnaire¹⁹,
- ICS habit strength, measured using the Habit Strength Index adapted for asthma controller use²⁰.

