4.16.2 Efficacy Analysis

We will assess the effectiveness of randomization by comparing the study arm balance on key demographic, clinical, and past health care utilization variables using analysis of variance (ANOVA) and t-tests or the nonparametric equivalent for continuous variables and chi-square tests or Fisher exact tests for categorical variables.

Primary analysis: Our primary outcome will be monthly ICS adherence in months 0-3 (Experiment Phase). Secondary outcomes will include monthly ICS adherence in months 4-6 (Observation Phase), asthma control at the end of the Experiment and Observation period. Secondary outcomes will also include monthly ICS adherence in months 7-13 (follow up period) to assess feasibility and acceptability of longer durations of electronic monitoring. We will consider arcsine transformation on the ICS adherence outcomes as necessary. This technique is commonly used for proportion data. We will use generalized estimating equations (GEE) to adjust for within-subject correlations due to repeated measures for the study's primary and secondary monthly adherence outcomes. Models will include main effects for arm and time (month) and arm-by-month interaction terms to allow for differing ICS adherence over time between arms. The dependent variable of monthly ICS adherence will be defined as mean daily observed-to-prescribed ICS actuation proportion for each study month. Mean daily adherence proportion will be capped at 1, such that participants taking more than their prescribed daily dose cannot receive "extra credit" for doses taken on those days. All statistical tests will be 2-sided. A P-value <0.05 will be considered statistically significant.

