4.18 Additional analyses

Hypothesis 1.2 Longer time intervals to next asthma-related ED or inpatient visit, and reduced healthcare use and costs, will be observed in Arm 1 compared to Arms 2 and 3 (and in Arm 2 compared to Arm 3).

Time to next asthma-related ED or inpatient visit from enrollment will be first modeled using the Kaplan-Meier plots. Study arms will be compared using log-rank tests and unadjusted Cox proportion hazards models. Adjusted hazard models will include the additional covariates described above and the Anderson-Gill method will be used to account for recurrent events. Total medical costs will be estimated for the 12 months following study enrollment, accounting for each asthma-related ED visit and hospitalization, as well as the expenses incurred with study participant incentives, sensors, and use of the WTH automated platform. We predict that intervention will reduce medical costs, thereby contributing to a *cost offset*. We will estimate potential savings in medical costs by calculating the difference in average total medical costs minus study-related expenses between study arms.

Aim 2. Assess proposed mechanisms by which intervention strategy influenced adherence trajectory.

Aim overview: The broad goal of this aim is to assess which participant and study characteristics are associated with different longitudinal adherence trajectories.

Characteristics to be examined include baseline factors (demographic, clinical, and prior health utilization factors), intervention strategy (study arm), and potentially modifiable behavioral characteristics. Of specific interest is how intervention strategy in the Experiment phase (study arm) influences child asthma self-efficacy, shared medication responsibility, and medication habit over time and how these characteristics vary with longitudinal ICS adherence trajectories. [Figure 4]

Hypothesis 2: Increases in (1) participant self-efficacy, (2) shared medication responsibility, and (3) habit score will partially mediate the relationship between study arm and sustained adherence trajectory.

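### Section 4.18 does not state that the Aim 2 mediation models adjust for each mediator's Visit 1 score or for run-in adherence, so differences that existed at entry can inflate the percentage mediated.

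*Combined protocol and SAP*

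**What the plan says.** Hypothesis 2 (section 4.18) holds that rises in self-efficacy, shared medication responsibility and habit score partly mediate the effect of arm on sustained adherence.

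- **Model terms.** The multivariable trajectory model is built in the order "first including (1) baseline demographic and clinical characteristics, then (2) study arm, and lastly, (3) the three hypothesized potential mechanisms". The Aim 2 overview describes the baseline set: "Characteristics to be examined include baseline factors (demographic, clinical, and prior health utilization factors". Neither place names the Visit 1 mediator scores or run-in adherence.
- **Screening and output.** Variables with a bivariate P above 0.2 are dropped. Mediation is run on variables associated with both arm and trajectory, and the share of the arm effect that is mediated is then calculated.
- **Visit 1 scores exist.** Section 4.11.2 says that the three scales, or question blocks from them, "will be used to assess key constructs at each study visit", and section 4.2 lists those blocks for Visit 1.
- **Baseline adherence exists.** Section 3.1.2 states: "The second two weeks of the Run-in Phase is designed to provide baseline adherence data". The analysis sections (4.16 to 4.18) do not say that it enters a model.
- **Both precede the intervention.** Under section 4.4, families do not learn their arm until the Experiment phase begins.

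Section 4.18 does not say whether the follow-up score or the change from Visit 1 is entered, or which visit supplies it.

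**The concern.** A mediated effect is the product of two paths. Randomization makes the first, arm to mediator, a fair comparison. It does nothing for the second, mediator to trajectory, because families are not randomized to a habit score. A family with a firm ICS routine at entry will tend to score higher on habit later and also to adhere better. If nothing in the model represents where the family started, the mediator coefficient absorbs that association. Multiplied by a real effect of arm on the mediator, it becomes an apparent mediated effect even when the mediator does nothing.

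At stake is the main quantitative output of Aim 2. A spurious percentage could lead a later trial to target a mechanism that does not drive adherence.

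**Working it through.** **The plan's own figure.** There is none for the mediation analysis. The only sample-size figure concerns arms 1 and 3: "To ensure a power of 80% at a significance level of 0.05", "corresponding to 65% and 35%, respectively), 40 patients are required in each of these two arms", "we estimate ~20% loss to follow-up". It reproduces: (1.960 + 0.842)² × (0.65×0.35 + 0.35×0.65) / 0.30² = 39.7, so 40 per arm; 40/0.80 = 50; 50 + 25 + 50 = 125. It is used below only to set 80 completers in arms 1 and 3.

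**Assumed inputs (not in the documents).** The mediator has no effect on adherence. The arm raises adherence by 1 SD and the mediator by a = 0.5 SD. The within-arm correlation of the mediator at Visit 1 and follow-up is r = 0.3 to 0.7. The correlation of the Visit 1 score with later adherence is q = 0.3 to 0.5. Outcomes are continuous, to keep the algebra visible. The total effect is 1, so the percentage mediated is a times the mediator coefficient.

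**Case A: the Visit 1 score is itself the confounder, without error.**
- Follow-up score, unadjusted: coefficient r×q. Percentage = a×r×q, from 0.5×0.3×0.3 = 4.5% to 0.5×0.7×0.5 = 17.5%.
- Visit 1 score added: 0%.
- Raw change, unadjusted: coefficient −q/2. Percentage = −a×q/2, from −0.5×0.3/2 = −7.5% to −0.5×0.5/2 = −12.5%.

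**Case B: a stable family trait drives adherence and both mediator scores, each score measuring it with error.** The trait's share of mediator variance equals r. Run-in adherence measures the same trait with share s = 0.5 to 0.7.
- Follow-up score, unadjusted: coefficient q. Percentage = a×q, from 0.5×0.3 = 15% to 0.5×0.5 = 25%.
- Visit 1 score added: a×q/(1+r), from 0.15/1.7 = 8.8% to 0.25/1.3 = 19.2%.
- Both baselines added: a×q/(1−r) divided by [1 + 2r/(1−r) + s/(1−s)]. With r = 0.3, s = 0.7, q = 0.3: 0.214/4.19 = 5.1%. With s = 0.5 the expression reduces to a×q/2 for any r, so q = 0.5 gives 12.5%. The range is about 5% to 13%.
- Raw change, unadjusted: the trait cancels, about 0%.

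Simulations of both cases at n = 400,000 agree with these formulas to within 0.3 percentage points.

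**Case C: binary sustained-adherence outcome, closer to the plan.** Trait model with logistic outcome, trait log-odds 1.0, arm log-odds 1.25, trait share 0.5 to 0.7, no true mediation. A false finding means both paths significant, using the level in section 4.16.2: "All statistical tests will be 2-sided. A P-value <0.05 will be considered statistically significant". There were 80 children per trial and 1,500 trials per setting.

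| Arm effect on mediator | Model | Falsely mediated | False joint finding |
|---|---|---|---|
| 0 | as listed | about 0% | 4% to 5% |
| 0.5 SD | as listed | 29% to 34% | 45% to 52% |
| 0.5 SD | both baselines added | about 14% | 11% to 15% |
| 0.5 SD | raw change, unadjusted | under 1% | about 4% |
| 0.3 to 0.8 SD | as listed | 17% to 53% | 18% to 82% |
| 0.3 to 0.8 SD | both baselines added | 8% to 22% | 6% to 18% |

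The larger percentages reflect the trait effect chosen here. The ordering of the models matches Case B.

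**Change or follow-up once Visit 1 is in the model.** Let M1 be the follow-up score, M0 the Visit 1 score and D = M1 − M0. Then b1×M1 + b0×M0 = b1×D + (b1 + b0)×M0. The mediator coefficient b1 is the same either way. So is the arm coefficient in the mediator model, since subtracting M0 from the outcome of a regression that contains M0 shifts only the M0 coefficient. The mediated effect is therefore identical.

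**The case against.** The strongest reply is that Hypothesis 2 is worded as increases, which points to change scores, and that a stable additive family difference cancels in a change score. That is correct for Cases B and C. It does not settle the matter. Section 4.18 never carries the change form into the model, and in Case A unadjusted change is biased by −7.5% to −12.5%. The result depends on a choice the plan leaves open.

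Four stronger readings are tempting but not supported:

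- **That the plan rules out adjustment.** Section 4.18 refers to a Covariates section that does not appear in the text available, and the clinical characteristics are not itemised. The supportable statement is that the plan does not state that it adjusts.
- **That adding the Visit 1 score removes the bias.** This holds only if that score fully captures the confounder. With a trait measured with error, some false mediation remains even with both baselines.
- **That change scores always reverse the sign, or must be avoided.** The bias ranges from about 0 to negative depending on the model, and once the Visit 1 score is included the choice makes no difference.
- **That false mediation arises whatever the arm does.** On average it needs the arm to move the mediator; with no arm effect it is about 0%. The plan does, however, select mediators that are associated with arm.

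It is also fair to say that extra covariates strain a multinomial model in a trial of this size. That stands and is dealt with in the fix.

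**Conclusion.** The concern holds as a gap in specification that has a direction. A model following the list in section 4.18, with follow-up scores entered, leaves the mediator-to-trajectory path open to confounding by differences that existed at entry, although two measures of those differences are already in hand. In the continuous-outcome illustration at a = 0.5 SD, false mediation is about 5% to 25% without adjustment. Adjustment brings it to 0 if the Visit 1 score is the confounder, and to about 5% to 13% with both baselines if the confounder is a trait measured with error. Only the mechanism follows from the design; every size rests on assumed correlations, and the logistic version gives larger values under its own assumptions.

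The consequence is confined to Aim 2, a secondary objective. Nothing here bears on the primary comparison of arms 1 and 3 or on its sample size.

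**What to change.** In section 4.18:

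1. Force the Visit 1 score of the mediator and mean adherence in run-in weeks 3-4 into every mediator model and every trajectory model used for mediation, exempt from the P > 0.2 screen.
2. State the visit at which each mediator is taken. With the Visit 1 score in the model, follow-up and change give the same mediator coefficient, so either may be entered.
3. Report the percentage mediated as still open to residual confounding.

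The cost is wording only; no new data are needed. The statistical price is two more covariates per equation. With 2 to 5 trajectory groups that means 2×(2−1) = 2 to 2×(5−1) = 8 more coefficients in the multinomial model. The plan's example minimum of more than 5% of the sample is 0.05×125 = 6.25, so a group could hold as few as 7 children and estimates could be unstable. If groups are sparse, collapse the outcome to sustained versus non-sustained, a split that section 4.18 already uses for Aim 3.

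### Mediation is to be summarised as a percentage of the total arm effect, a ratio that is unstable for Arm 2 vs Arm 3 and imprecise even for Arm 1 vs Arm 3, with no interval or reporting rule stated

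*Combined protocol and SAP*

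**What the plan says.** Hypothesis 2 (section 4.18, Aim 2) is that gains in self-efficacy, shared responsibility and habit "will partially mediate the relationship between study arm and sustained adherence trajectory". The outcome is trajectory group, modelled by multinomial or ordered logistic regression: "I will then construct a final multivariable multinomial regression model of trajectory of all marginally predictive covariates". A selection step comes before the mediation analysis: "Mediation analysis will be conducted with variables associated with both study arm and trajectory membership". No threshold is given for being associated.

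Coefficients are then standardized "to obtain an overall mediated effect of each potential mechanism variable (e.g. child self-efficacy) on each study arm", and the amount mediated is summarised as a ratio: "The percentage of the total effect of study arm that is mediated by child self-efficacy, for instance, will be calculated using standardized beta estimates". Section 4.18 mentions no interval for this percentage. It does not say what is reported if the total effect is close to zero or runs the wrong way.

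On contrasts, section 4.16.2 says of the trajectory model that "relative risk ratios for arms 1 and 2 compared to arm 3 will be calculated", so Arm 2 vs Arm 3 is in scope. Section 4.17 gives 50, 25 and 50 children in Arms 1, 2 and 3, expects about 20% loss, and adds: "The study is not to be powered to detect differences in arms 1 to 2 or 2 to 3".

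**The concern.** The percentage mediated has the total arm effect as its denominator. When the sampling distribution of that effect puts real weight near zero or on the wrong side of it, the ratio can be negative, exceed 100%, or be very large for reasons unrelated to mediation. Arm 2 vs Arm 3 is exposed to this because Arm 2 is half the size of the other arms and the plan concedes that the contrast is not powered.

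Standardizing the coefficients helps with comparing logistic coefficients across models. It does not help here: in the product form a common scale factor appears in numerator and denominator and cancels, so a weak denominator stays weak.

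At stake is how Hypothesis 2 is answered. Partial mediation means a share between 0% and 100%. A reported share of -40% or 170% cannot be read against that hypothesis, and a plausible-looking 60% could come from a true 30%. Section 4.17 wants preliminary estimates of component effects to plan a later multicentre study, so the figure may be carried forward.

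**Working it through.** **1. The plan's own figure.** The documents give no formula for the sample size. Two proportions with unpooled variance, two-sided 0.05 and 80% power, reproduce it:

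n = (1.960 + 0.842)² × (0.65×0.35 + 0.35×0.65) / 0.30² = 7.85 × 0.455 / 0.09 = 39.7, so 40 per arm.

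40 / 0.80 = 50 enrolled. For Arm 2, 25 × 0.80 = 20 after loss.

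**2. How weak the Arm 2 denominator is.** The documents give no expected Arm 2 value. Assume 50%, midway between 65% and 35%, which makes Arm 2 vs Arm 3 a 15-point difference.

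- 25 vs 50 children: SE = √(0.50×0.50/25 + 0.35×0.65/50) = 0.121. Then 0.15/0.121 = 1.24, power is about 24%, and the chance of a wrong-signed estimate is 10.7%.
- 20 vs 40 children: SE = 0.135, ratio 1.11, power about 20%, wrong sign 13.3%.
- Arm 1 vs Arm 3, 30 points: wrong sign 0.1-0.3%.

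**3. Simulation of the percentage.** The documents give no mediator effect and no mediated share, so these inputs are assumptions. The mediator is M = a·A + N(0,1). The outcome is logit P(sustained) = -1.2 + c·A + b·M. The reported figure is 100 × ab/(ab + c), with a, b and c estimated.

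- Arm 1 vs 3: a = 0.4, b = 0.9, c = 0.84, so 0.36/(0.36 + 0.84) = 30%.
- Arm 2 vs 3: a = 0.2, b = 0.9, c = 0.42, so 0.18/(0.18 + 0.42) = 30%.

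These imply 26%, 37% and 50% sustained in Arms 3, 2 and 1. Results from 3,000 trials per scenario:

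| Contrast (children) | Outside 0-100% | Outside, after selection at p<0.05 |
|---|---|---|
| Arm 2 vs 3 (20 vs 40) | 37% | about 34% |
| Arm 2 vs 3 (25 vs 50) | 32-34% | about 24% |
| Arm 2 vs 3 (20 vs 40), Arm 2 responding as Arm 1 | 16% | 14% |
| Arm 1 vs 3 (40 vs 40) | 8% | 6% |

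For Arm 2 vs 3 at 20 vs 40, 26% of estimates are negative, and the total effect has the wrong sign in 18%. The 5th percentile is about -120%, and the 95th moves between roughly 180% and 210% from run to run. For Arm 1 vs 3 the 5th-95th percentile is about 1% to 88%.

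**4. Effect of the selection step.** The p<0.05 threshold is my assumption, applied to both associations within the contrast. About 9% of Arm 2 vs 3 trials at 20 vs 40 then reach the mediation step. That is about 270 of 3,000, so a rate near 30% carries a Monte Carlo SE of √(0.3×0.7/270) = 2.8 points. Among trials that pass, 24-34% are still out of range. The median reported share rises to about 56-61% for Arm 2 vs 3 and about 40% for Arm 1 vs 3, against a true 30%.

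**5. Wider assumptions.** I varied the mediated share (20%, 30%, 50%), the mediator slope (0.4 to 1.2 on the log-odds scale), the sizes (50/25/50 and 40/20/40), the frequency of sustained adherence, and the outcome model (binary, or three-group multinomial).

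| Setting | Outside 0-100% |
|---|---|
| Arm 2 midway, binary | 21-41% (after selection 20-35%) |
| Arm 2 midway, multinomial | 25-42% (after selection 24-42%) |
| Arm 2 off the midpoint (60% or 40%), closer contrast | 44-52% |
| Arm 2 off the midpoint, wider contrast | 9-24% |
| Arm 1 vs 3 | 2-20% |

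Covariates and trajectory misclassification were left out.

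**The case against.** The best defence is that the plan limits its own exposure. Mediation is run only for variables associated with both arm and trajectory, the Arm 2 contrasts are declared unpowered, and the analysis belongs to a secondary aim on which no primary result depends. All of that stands and keeps the weight of the point low. But the selection step lowers the out-of-range rate only modestly and pushes the surviving estimates upward. If association is judged across all three arms, a mediator could qualify on Arm 1's effect alone and still yield a percentage for Arm 2.

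It is also fair that the missing interval is an inference from silence. The sentence cites a method source, but that number in the reference list is a review of reminder systems, so the source cannot be identified. It may include an interval. Section 4.18 does not say so.

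Several stronger readings are tempting and do not hold:

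- A reader might infer that a trial of this size gives an impossible percentage more than a third of the time. Size alone does not fix the rate. It depends on the Arm 2 response, the mediator strength and the mediated share, none of which the documents give, and it is often below one third.
- A reader might cite the case of no mediation in Arm 2 vs 3, where 48% of estimates fall outside 0-100%. About 41 of those 48 points are negative values scattered around a true zero. Arm 1 vs 3 with no mediation gives 52% outside even though its 5th-95th percentile is only -48% to 30%. That count says little about instability.
- A reader might extend the point to a planned Arm 1 vs Arm 2 percentage. Section 4.16.2 lists ratios against Arm 3 only, and section 4.18 does not clearly promise a percentage for every contrast.

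**Conclusion.** The concern holds in a limited form. The summary chosen for Hypothesis 2 is unstable for Arm 2 vs Arm 3: out of range in roughly a quarter to two fifths of trials if Arm 2 is about midway, and in about 9-52% more widely. For Arm 1 vs Arm 3 it is usually in range (8% outside at 40 per arm with a true 30%) but imprecise. These rates rest on assumed inputs. The instability itself does not, since it follows from dividing by an effect that the trial is not sized to estimate.

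It would go too far to conclude that Aim 2 as a whole cannot be interpreted. The trouble lies mainly with Arm 2, and the contrast for which the trial is sized remains usable if its uncertainty is shown. This is a cheap improvement to a secondary aim and does not threaten the primary result.

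**What to change.** In section 4.18:

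- Name Arm 1 vs Arm 3 as the mediation contrast.
- Report the indirect and direct effects on the probability of the sustained trajectory as risk differences, by standardization from the same mediator and outcome regressions. Give each a 95% interval from a bootstrap that resamples children. Under the inputs in step 3, the Arm 1 vs Arm 3 indirect effect has a median of 7 percentage points and a 5th-95th percentile of 0 to 17, with no unstable denominator.
- Quote a percentage mediated only with its bootstrap interval, and only when the interval for the total effect excludes zero.
- For contrasts with Arm 2, report the effects with intervals and no percentage.

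The cost is plan wording, modest programming and a less simple headline figure. No new data are needed.
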